Cover Page

ID: 5160230

Benefit of Adding Stretching to Standard
Intervention for Patients with
Nonspecific Mechanical Neck Pain

NCT03194490

Date: October 09, 2019

Methods

Participants

Forty-three participants who had at least two weeks of non-specific mechanical neck pain were randomly assigned to either the combined intervention (passive cervical mobilization, active range of motion exercises, and stretching techniques) ($n_1=20$) or standard intervention group (passive cervical mobilization and active range of motion exercises) ($n_2=23$). At two-weeks follow-up, 2 participants dropped out of the study due to health conditions, and at 8 weeks, 3 participants withdrew. (Refer to Figure 1) Thus, 38 participants with a mean age 31.0 ± 8.3 years, height 1.6 ± 0.1 m, mass 72.8 ± 17.5 kg, and body mass index 26.9 ± 6.7 kg/m² completed this study. All participants read and signed a consent form that was approved by the institutional review board at Loma Linda University. This study was registered in ClinicalTrials.gov with Protocol #5160230. The participants met the following inclusion criteria: between 18 and 60 years of age, had non-specific neck pain for at least 2 weeks, and pain intensity of more than 2 points on a numeric pain rating scale (NPRS) in the past week. Participants were excluded from the study if they had one or more of the following conditions: specific diagnosis of the cervical spine, such as spinal stenosis, disc prolapse, previous surgery in the neck and shoulder areas, shoulder pathology (bursitis, tendonitis, adhesive capsulitis), history of severe trauma, ligamentous instability, hypermobility syndrome, migraine (frequency more than twice per month), spasmodic torticollis, radiculopathy due to peripheral nerve entrapment, fibromyalgia, severe psychiatric illness, inflammatory rheumatic diseases, pregnancy or other on-going therapies.

The identification of the study's excluding criteria was conducted through clinical examination, medical history and self-reported questionnaires ⁶. Participants were randomly assigned to either the combined intervention group or the standard intervention group using a random number table. Demographic and general characteristics of the participants are presented in **Table 1**.

Instrumentation

Cervical ROM

The Gravity Inclinometer method using the Cervical ROM Device (CROM) was used to assess active ROM for flexion, extension, lateral flexion, and rotation. The CROM was used in many clinical trials and deemed to have good reliability and validity ¹⁹. Lee, Nicholson, Adams ²⁰ indicated that the cervical ROM device has high intra-examiner reliability with an ICC of 0.84 (95% CI: 0.72;0.91) for flexion, an ICC of 0.81 (95% CI: 0.67;0.89) for extension, an ICC of 0.81 (95% CI: 0.66; 0.89) for right lateral flexion, an ICC of 0.81 (95% CI: 0.68; 0.90) for left lateral flexion, an ICC of 0.74 (95% CI: 0.56;0.85) for right rotation, and an ICC of 0.76 (95% CI: 0.59;0.86) for left rotation. The CROM device has high concurrent validity compared to

radiograph ²¹. William et al. (2010) reported that CROM has high validity with correlation coefficients of 0.97 for flexion and 0.98 for extension.

In order to measure cervical ROM, the participant sat on a stool facing the west, feet flat on floor, and arms hanging at each side. One examiner positioned the CROM device on the participant's head. Then 3 trials were recorded for six different direction: flexion, extension, right and left lateral flexion, and left and right rotation. The other examiner then recorded the average of the three trails for each position.

Pressure Pain Threshold

The digital algometer is an electronic device used to measure the amount of force that is required to produce pain or pressure pain threshold (PPT) ²². It has high reliability and validity in measuring pain threshold for individuals with neck pain. Park, Kim, Park, Kim, Jang ²³ indicated that pressure pain threshold has a high intra rater reliability ranging from 0.94 to 0.98. The validity of the electric algometer ranged from 0.95 to 0.98 ²⁴.

In order to measure neck pressure pain threshold, a handheld electronic pressure algometer with a surface area at the round tip of 1 cm² was utilized. The participant laid prone on a treatment table and was instructed to report the first point when pressure sensation turned into pain sensation. The examiner increased the pressure gradually at rate of 1 kg/sec perpendicularly to the right upper trapezius at the upper border of muscle between the lateral border of acromion and the midline and then on the left side with a 30-second pause between each trial ²². Three trials were performed at each side in each test session ²⁵.

Numeric pain rating scale

Numeric pain rating scale (NPRS) was used to determine the level of the participant's pain. It consists of a straight 100 mm line that is scored from 0 to 10 with 10 mm intervals. The zero represents no pain while a 10 represents very severe pain. The Numeric pain rating scale has moderate reliability with correlation coefficients ranging from 0.60 to 0.77 ²⁶. In addition, Boonstra, Preuper, Reneman, Posthumus, Stewart ²⁶ indicated that NPRS has high validity in detecting pain with correlation coefficients ranging from 0.64 to 0.84.

Neck Disability Index

The Neck Disability Index (NDI) consists of ten items that each range from 0 to 5 that help measure the level of disability for patients with neck pain. The NDI score ranges from 0 to 50 ²⁷. The level of disability determined by the score of NDI is as follows: 0 - 4 = no disability, 5 - 14 = mild, 15 - 24 = moderate, 25 - 34 = severe, and above 34 = complete disability ²⁷. The NDI has a high test-retest reliability with an intra class correlation (ICC) between 0.88 and 0.95 and high internal consistency with Cronbach's α values ranging from 0.85 to 0.90 ²⁸. For NDI score, the ICC was 0.83 (95% CI, 0.75–0.90), which indicates that the NDI has high validity to detect any

small change in the patient's condition²⁹. In addition, Childs, Cleland, Elliott, Teyhen, Wainner, Whitman, Sopky, Godges, Flynn, Delitto¹⁸ reported that NDI has high sensitivity and specificity of 0.83 and 0.72, respectively.

Global rating of change

The Global Rating of Change was used to measure the amount of improvement that the patient achieves from the intervention or rehabilitation program. The score ranges from -7 to 7 in which -/+3 to -/+ 1 represents a small change, -/+ 4 to -/+5 represents moderate change and -/+6 to -/+7 means a large change. The negative and positive signs determine whether the patient's condition worsens or improves respectively. GROC has a high test-retest reliability with an ICC value of 0.90 (95% confidence interval (CI) 0.84 to 0.93). In addition, GROC has high face validity with Pearson's $r = 0.72 - 0.90$ and $ICC = 0.74$ ³⁰. Kamper, Maher, Mackay³⁰ reported that the GROC has high construct validity when compared to other gold standard measurements such as the Roland Morris, Oswestry, and pain rating scale.

Procedures:

The study was conducted over 8 weeks. Participants were randomly allocated into two groups: *combined intervention* (passive cervical mobilization, active range of motion exercises, and stretching techniques) ($n_1=18$) and *standard intervention groups* ($n_2=20$). The randomization was performed by a person who was blind to the patient's allocation. Participants in the *combined intervention group* received 30 minutes of passive manual therapy consists of (i) cervical mobilization and (ii) active cervical range of motion exercises to be performed at home 3-4 times daily, (iii) stretching techniques for 2 sessions per week for 4 weeks (iv) a self-administered stretching exercises to be performed at home 5 times a week. Participants in *standard intervention group* received 15 minutes of manual therapy consists of (i) cervical mobilization and (ii) active range of motion exercises to be performed at home 3-4 times daily.

Cervical Mobilization techniques were used in the study and consisted of low-velocity non-thrust cervical joint mobilizations for unilateral symptoms: postero-anterior unilateral vertebral pressure, traction, and transfer vertebral pressure. For bilateral symptoms, the following joint mobilization were applied: postero-anterior central vertebral pressure, postero-anterior unilateral vertebral pressure (2 sides), longitudinal movement, traction and rotation. These techniques have been described previously by Anandacoomarasamy, Barnsley³¹. Both groups received 10 minutes of cervical mobilization for 2 sessions per week for 4 weeks.

Active Cervical Range of Motion Exercises (ACROM) were performed 10 repetitions 3–4 times daily. The ACROM exercise consisted of the subject placing four fingers over the manubrium bone and placing chin on the fingers. The subject was then instructed to rotate to one side as far as possible and return to neutral and then actively rotate to the other side³². Both groups performed ACROM exercises. Subjects were advised to maintain their usual activity within the limits of pain.

Stretching techniques were performed in the combined intervention group for 30 seconds for each muscle and repeated 3 times twice a week to the following muscles: anterior, middle and posterior scalene, upper fibers of trapezius, pectoralis minor muscles and interspinous muscles as described by Ylinen, Chaitow, Nurmenniemi, Hill ³³.

The cervical mobilization and stretching exercise techniques were performed by a licensed physical therapist who has 6 years of experience in manual physical therapy.

Self-administered stretching exercises were performed by participants in the combined intervention group to the following muscles: the extensor muscles, the upper part of the trapezius, and the posterior scalene ⁶. Each movement was held for 30 seconds and repeated 3 times. Lastly, the participant was instructed to perform a neck straightening exercise by retracting the neck (Chin tuck) 5 times for 3-5 seconds. Subjects in the combined intervention group were provided with written instruction of the stretching exercises and directed to perform stretching exercise 5 times a week, each exercise session takes about 10 minutes. Patients were also instructed to keep a stretching diary to track their stretch exercise frequency.

Data collection:

Data was collected at baseline, one week after intervention, and week 4. The final data collection date was set at week 8 as a follow up to determine whether the participant was able to maintain gains at one month following the interventions.

Statistical Analyses

A sample size of 50 participants was estimated using a moderate effect size of 0.25, level of significance 0.05, and power of 0.80. Data was summarized using mean and standard deviation ¹ for quantitative variables and counts (%) for qualitative variables. The normality of continuous variables was examined using Shapiro Wilk's test. The distribution of the participants' characteristics by study group were evaluated using chi-square for qualitative variables and independent t- test for quantitative variables. Mixed factorial analysis of variance (ANOVA) was used to examine changes in cervical ROM variables, pressure pain threshold, NPRS, GROC, and NDI scores by study group over time. Post hoc comparisons using Bonferroni test and effect size were computed to identify significant differences over time. We compared percent change (4 weeks vs. baseline) for all outcome variables between the two study groups using independent t- test and Mann- Whitney test. To examine whether there were any changes in the outcome variables at 4 weeks follow up paired t- test was used. The level of significance was set at $p \leq 0.05$. Statistical analysis was performed using IBM SPSS Software version 24 for Windows (Chicago, IL, USA).

Results

Thirty-eight (38) subjects with a mean \pm SD age 30.9 ± 8.1 years and body mass index (BMI) 26.8 ± 6.7 kg/m² participated in the study. Sixty- five percent of the participants were females (n=

26). There was no significant difference between the two study groups in terms of age, Body Mass Index (BMI), cervical ROM and pressure pain threshold at baseline. Demographic and general characteristics are presented in **Table 1**.

Changes in ROM

Results of the mixed factorial ANOVA for ROM is displayed in **Table 2**. There was a significant difference in mean ROM during extension over time ($F_{2,72}=6.8$, $p=0.002$, $\eta^2=0.20$), and a significant group by time interaction ($F_{2,72}=3.6$, $p=0.02$). Bonferroni post hoc comparison revealed that the difference was significant between baseline and one week later (70.2 ± 2.1 vs. 74.3 ± 2.4 , $p=0.04$), baseline and 4 weeks later (70.2 ± 2.1 vs. 76.6 ± 2.0 , $p=0.001$), however, there was no significant difference between one week later and 4 weeks ($p=0.15$). In addition, the % improvement from baseline to 4 weeks later was significantly different between the combined intervention and standard intervention groups respectively (18.9% vs. 3.0% ; $t=2.4$, $p=0.02$). (Refer to **Table 2**)

Also, there was a significant difference in mean ROM during right lateral flexion over time ($F_{2,72}=13.8$, $p<0.001$, $\eta^2=0.30$), and a significant group by time interaction ($F_{2,72}=2.9$, $p=0.04$). Bonferroni post hoc comparison revealed that the difference was significant between baseline and one week later (40.8 ± 1.5 vs. 43.8 ± 1.3 , $p=0.03$), baseline and 4 weeks later (40.8 ± 1.5 vs. 46.8 ± 1.4 , $p<0.001$), and between one week later and 4 weeks (43.8 ± 1.3 vs. 46.8 ± 1.4 , $p=0.001$). In addition, the % improvement from baseline to 4 weeks later was significantly different between the combined intervention and groups respectively (23.2% vs. 10.8% ; $t=1.8$, $p=0.04$). (Refer to **Table 2**).

There was a significant difference in mean ROM during left lateral flexion over time ($F_{2,72}=3.0$, $p=0.03$, $\eta^2=0.30$), and a significant group by time interaction ($F_{2,72}=3.0$, $p=0.03$). Bonferroni post hoc comparison revealed that the difference was significant between baseline and one week later (43.0 ± 1.1 vs. 46.3 ± 1.0 , $p=0.01$), baseline and 4 weeks later (43.0 ± 1.1 vs. 48.5 ± 1.3 , $p<0.001$), and between one week later and 4 weeks (46.3 ± 1.0 vs. 48.5 ± 1.3 , $p=0.01$). In addition, the percent improvement from baseline to 4 weeks later was significantly more for the combined intervention as compared to the standard intervention group (20.0% vs. 7.7% ; $t=2.1$, $p=0.02$).

For the other ROM directions, flexion, right rotation, and left rotation, both groups had a significant improvement in mean ROM over time ($p<0.05$), however, this improvement was not significantly different between the two groups. (Refer to **Table 2**).

Change in Pressure Pain Threshold (PPT)

There was a significant difference in mean right upper trapezius muscle pressure pain threshold over time ($F_{2,72}=4.3$, $p=0.02$, $\eta^2=0.11$), however, there was no significant group by time

interaction ($F_{2,72}=0.98$, $p=0.38$), and the change over time was not significantly different between the two groups ($F_{2,72}=0.02$, $p=0.90$). Bonferroni post hoc comparison revealed that the difference was significant between baseline and 4 weeks later (4.7 ± 0.3 vs. 5.5 ± 0.3 , $p=0.01$), and between one week later and 4 weeks (4.7 ± 0.3 vs. 5.5 ± 0.3 , $p=0.01$). For left pressure pain threshold, there was a significant difference over time ($F_{2,72}=8.4$, $p=0.001$, $\eta^2=0.20$), however, there was no significant group by time interaction ($F_{2,72}=0.48$, $p=0.59$), and the change over time was not significantly different between the two groups ($F_{2,72}=0.02$, $p=0.86$). Bonferroni post hoc comparison revealed that the difference was significant between baseline and 4 weeks later (4.5 ± 0.3 vs. 5.7 ± 0.4 , $p=0.005$), and between one week later and 4 weeks (4.5 ± 0.2 vs. 5.7 ± 0.4 , $p=0.001$). (Refer to **Table 3**).

Changes in NPRS

There was a significant difference in mean NPRS over time ($F_{2,72}=47.8$, $p<0.001$, $\eta^2=0.60$), however, there was no significant group by time interaction ($F_{2,72}=1.5$, $p=0.23$), and the improvement did not differ significantly by study group ($F_{1,36}=1.4$, $p=0.24$). Bonferroni post hoc comparison revealed that the difference was significant between baseline and one week later (4.7 ± 0.3 vs. 3.3 ± 0.3 , $p<0.001$), baseline and 4 weeks later (4.7 ± 0.3 vs. 1.7 ± 0.3 , $p<0.001$), and between one week later and 4 weeks (3.3 ± 0.3 vs. 1.7 ± 0.3 , $p<0.001$).

Change in GROG

For GROG, there was a significant difference over time ($F_{1,36}=42.9$, $p<0.001$, $\eta^2=0.54$), however, there was no significant group by time interaction ($F_{1,36}=0.001$, $p=0.98$), and the improvement was not significantly different by study group ($F_{1,36}=0.7$, $p=0.40$). Bonferroni post hoc comparison revealed that the difference was significant between one week later and 4 weeks (2.4 ± 0.3 vs. 4.7 ± 0.4 , $p<0.001$). (Refer to **Table 3**).

Change in NDI

There was a significant difference in mean NDI over time ($F_{2,72}=38.2$, $p<0.001$, $\eta^2=0.52$), however, there was no significant group by time interaction ($F_{2,72}=2.8$, $p=0.07$), and the improvement over time did not differ by study group ($F_{1,36}=0.0$, $p=0.98$). Bonferroni post hoc comparison revealed that the difference was significant between baseline and one week later (11.2 ± 0.8 vs. 7.6 ± 0.7 , $p<0.001$), baseline and 4 weeks later (11.2 ± 0.8 vs. 4.5 ± 0.8 , $p<0.001$), and between one week later and 4 weeks (7.6 ± 0.7 vs. 4.5 ± 0.8 , $p<0.001$). After 4 weeks follow up, there were no significant changes in all the outcome variables by study group. (Refer to **Table 4**)

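### The ANOVAs use the 38 completers of 43 randomised, and on the printed F and degrees of freedom two of the three ROM interactions called significant have p above 0.05

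*Combined protocol and SAP*

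**What the plan says.** **Who was analysed.** Methods (Participants) gives 20 randomised to the combined group ("stretching techniques) ($n_1=20$) or standard intervention group") and 23 to the standard group, 43 in all. It then states: "At two-weeks follow-up, 2 participants dropped out of the study due to health conditions, and at 8 weeks, 3 participants withdrew". That leaves 38. Procedures describes random allocation with other numbers: "n_1=18$) and *standard intervention groups* ($n_2=20". Results opens with "Thirty-eight (38) subjects with a mean" age and BMI. Statistical Analyses names a mixed factorial ANOVA and says nothing about missing data or about which participants are included.

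**Visits.** Data collection says: "Data was collected at baseline, one week after intervention, and week 4", with a final follow-up at week 8. A two-week visit is not listed.

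**Results claimed.** Under Changes in ROM, extension is reported with "a significant group by time interaction ($F_{2,72}=3.6$, $p=0.02"). Right lateral flexion has F(2,72)=2.9, p=0.04, and left lateral flexion has F(2,72)=3.0, p=0.03. The percent changes from baseline to week 4 are also called significant: t=2.4, p=0.02 (extension); t=1.8, p=0.04 (right); t=2.1, p=0.02 (left). Statistical Analyses plans to compare percent change "between the two study groups using independent t- test and Mann- Whitney test", at a level of 0.05, and mentions no one-sided test.

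**The concern.** There are two separate problems, and correcting one does not correct the other.

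1. **Analysis set.** The 38 are defined by staying to week 8, yet the ANOVA contrasts stop at week 4. The week-4 group comparison is therefore restricted by a later, post-randomisation event. Because Procedures prints the completer counts as the allocation, a reader of that section would not see that anyone is missing.
2. **Printed statistics.** The three ROM directions are the only outcomes for which the text reports a significant difference between groups. The interactions for pressure pain threshold, NPRS, GROC and NDI are all reported as non-significant. If the ROM p-values do not follow from their own test statistics, the evidence that stretching adds anything is weaker than stated.

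**Working it through.** **Step 1: number analysed.** The between-group error df is N - 2. Printed 36 gives N = 38. The within-subject error df at three visits is (N - 2) x 2 = 36 x 2 = 72, as printed. For GROC, with two visits, it is 36 x 1 = 36, as printed. All 43 would give 41 and 82. Left out: 20 - 18 = 2 (10%) and 23 - 20 = 3 (13%), together 5/43 = 11.6%.

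**Step 2: does the method reproduce the documents' own p-values?** The upper tail of F(2,72) gives:
- NDI interaction, F=2.8: 0.067 (printed 0.07)
- NPRS interaction, F=1.5: 0.230 (printed 0.23)
- Right pressure pain threshold interaction, F=0.98: 0.380 (printed 0.38)
- Extension time effect, F=6.8: 0.0020 (printed 0.002)

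These four agree.

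**Step 3: the three ROM interactions.** The 0.05 critical value of F(2,72) is 3.12. The range allows for rounding of F by ±0.05.

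| Direction | F | Printed p | p at F(2,72) | Range | p at F(3,108) |
|---|---|---|---|---|---|
| Extension | 3.6 | 0.02 | 0.032 | 0.031-0.034 | 0.016 |
| Right lateral flexion | 2.9 | 0.04 | 0.061 | 0.059-0.064 | 0.038 |
| Left lateral flexion | 3.0 | 0.03 | 0.056 | 0.054-0.059 | 0.034 |

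Rounding does not bring the last two to 0.05, and neither do the df for 43 people (2,82: 0.061 and 0.055). Compare the NDI interaction: F=2.8 is printed with p=0.07 and called non-significant, while F=2.9 on the same df is printed with p=0.04 and called significant.

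A sphericity correction would raise these values. With an assumed epsilon of 0.8 (the documents give none), F(1.6, 57.6) gives 0.043, 0.074 and 0.069.

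**Step 4: percent-change t-tests**, df = 38 - 2 = 36.

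| Direction | t | Printed p | Two-sided p (t ±0.05) | One-sided p |
|---|---|---|---|---|
| Extension | 2.4 | 0.02 | 0.022 (0.019-0.024) | 0.011 |
| Right lateral flexion | 1.8 | 0.04 | 0.080 (0.073-0.089) | 0.040 |
| Left lateral flexion | 2.1 | 0.02 | 0.043 (0.038-0.048) | 0.021 |

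Extension matches a two-sided test; the other two match one-sided tests. For right lateral flexion no choice of df helps: t=1.85 at df 1000 still gives a two-sided p of 0.065.

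**Step 5: what might be wrong.** All three interaction p-values fit F(3,108), the df for 38 people at four visits. Against that, the extension time effect fits F(2,72) and not F(3,108) (0.0003), and the post hoc contrasts list only three visits. For left lateral flexion, the time effect and the interaction carry the same F and p. Partial eta-squared from F=3.0 is (2 x 3.0)/(2 x 3.0 + 72) = 6/78 = 0.077, against a printed 0.30, which would need F = (0.30 x 72)/(0.70 x 2) = 15.4. At least one entry there is wrong.

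**The case against.** **The fault may lie in the df, not in p.** This stands as a limit. The p-values fit F(3,108), and other df are visibly misprinted. The between-group effects for pressure pain threshold are given as F(2,72)=0.02 with p=0.90 and 0.86, although a two-group effect has df (1,36). At (2,72) the p would be 0.98; at (1,36) it is 0.89 (0.875-0.903 with rounding). The left pressure pain threshold interaction (F=0.48, printed p=0.59) gives 0.62. The extension time effect prints eta-squared 0.20 where F=6.8 implies 0.159. Table 2, which might settle the matter, is not in the text available. So the check shows that F, df and p cannot all be right. It does not show that the true interactions are non-significant. The further misprints are more reason to reconcile the figures.

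**The percent-change p-values may be from the Mann-Whitney test.** That is possible, since both tests were planned, but they are printed beside t and not labelled otherwise.

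**The loss is small, nearly balanced and perhaps unavoidable.** In part this stands. With 10% and 13% lost, neither the direction nor the size of any bias can be given. If the five had no week-4 data, the week-4 comparison would be an ordinary complete-case one. Three of them left at 8 weeks, however, so their earlier data may exist and be unused. Figure 1, which might show this, is not in the text available.

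**Changing the main model after results are known is a matter of preference.** It is a change from the stated ANOVA and adds at most five people at week 4. Keeping the ANOVA alongside it lets readers see whether the choice matters.

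**Conclusion.** The concern holds. The ANOVAs leave out 5 of 43 randomised participants (12%) with no stated missing-data approach, and Procedures misstates the numbers allocated. The effect on the estimates is unknown.

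Taking the printed F, t and df at face value:
- **Right lateral flexion** has neither a significant interaction (0.061) nor a significant two-sided percent-change difference (0.080).
- **Left lateral flexion** has only the percent-change difference (0.043), not the interaction (0.056).
- **Extension** keeps both (0.032 and 0.022), without adjustment for the number of outcomes tested.

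Confidence is high that the printed statistics are inconsistent. Which figure is in error stays open until the original output is checked.

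**What to change.** 1. Rerun the ROM ANOVAs. State the visits in the model and any sphericity correction, and make F, df, p and eta-squared agree for every outcome, including the pressure pain threshold lines.
2. For each percent-change comparison, say whether p comes from the t-test or the Mann-Whitney test, and report it two-sided.
3. If the corrected p exceeds 0.05, withdraw the claim of a significant interaction for right and left lateral flexion, and of a significant percent-change difference for right lateral flexion.
4. Correct Procedures to 20 and 23 randomised.
5. Make the main comparison a likelihood-based mixed model using all available visits of all randomised participants in their assigned group, for example with baseline as one of the repeated outcomes (post-baseline visits only for GROC). Report between-group differences with 95% CIs at weeks 1, 4 and 8, and the change from week 4 to week 8 with its CI. Keep the 38-completer ANOVA as a sensitivity analysis.

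**Cost.** No new data, and a few hours of re-analysis in the same software. The mixed model assumes data are missing at random, it may add fewer than five people at week 4, and one or two significance claims may have to go.

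### The only stated power (0.80) belongs to 50 participants; 43 were randomised and 38 analysed, and the text gives no power or detectable effect for that size

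*Combined protocol and SAP*

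**What the plan says.** The combined protocol and SAP has one sample-size statement, in Statistical Analyses: "A sample size of 50 participants was estimated using a moderate effect size of 0.25, level of significance 0.05, and power of 0.80". It does not name the test, the effect-size metric, the number of visits, the correlation between visits or a dropout allowance. It also does not say whether 50 is a recruitment target or an analysis target.

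Methods, Participants, reports: "Forty-three participants who had at least two weeks of non-specific mechanical neck pain were randomly assigned", split 20 and 23. After five losses it continues: "Thus, 38 participants with a mean age". Procedures gives arms of 18 and 20. Results opens with "Thirty-eight (38) subjects with a mean".

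Several between-group findings are then reported as non-significant:

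- Flexion and both rotations (Changes in ROM): "this improvement was not significantly different between the two groups".
- Pressure pain threshold (PPT), both sides: for the right side, "the change over time was not significantly different between the two groups".
- NPRS: "the improvement did not differ significantly by study group".
- Global rating of change (GROC): no significant interaction or group effect.
- NDI: interaction p=0.07. The sentence on the group effect (p=0.98) says, without the qualifier about significance, that improvement was no different between groups.

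**The concern.** A reader who meets these null results and asks how well the trial could have detected a difference finds one figure, 0.80, and it describes a sample the trial did not have. Of the stated 50, 86% were randomised and 76% analysed. If the planning claim is taken at face value, the chance of missing the planned effect with 38 is about 0.32-0.33, not 0.20.

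This matters most where a non-significant result could be taken as evidence that added stretching makes no difference. NDI is the clearest case, because unqualified wording sits beside an interaction p-value of 0.07.

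**Working it through.** **1. Number analysed.** With two groups and three visits, the group x time error df is (N-2) x 2. The reported 72 gives N = 72/2 + 2 = 38. For GROC, with two visits, (N-2) x 1 = 36 also gives 38. Ratios: 43/50 = 0.86; 38/50 = 0.76; loss after randomisation 5/43 = 11.6%.

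**2. Can 50 be reproduced?** Not from what is stated. I read 0.25 as Cohen's f (an assumption) and use noncentral F power at alpha 0.05 with two groups, m visits and correlation rho:

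- group x time: lambda = f² N m / (1 - rho), df (m-1) and (N-2)(m-1)
- between groups: lambda = f² N m / (1 + (m-1) rho), df 1 and N-2

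At rho 0.5, the group x time test needs 34, 28 or 24 participants for m = 2, 3 or 4. The between-groups test needs 98, 86 or 82. Two visits with rho 0.25 does give 50 for group x time, but the document states neither input. So 50 is neither confirmed nor shown to be wrong.

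**3. Power at 43 and 38 on the plan's own premise.** Assume that 50 analysable participants give exactly 0.80. Set lambda = c x N, solve c so that N = 50 gives 0.80, then recompute for the group x time test:

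| Visits | lambda at 50 | lambda at 43 | lambda at 38 | Power at 43 | Power at 38 |
|---|---|---|---|---|---|
| 2 | 8.18 | 7.03 | 6.21 | 0.735 | 0.679 |
| 3 | 9.94 | 8.55 | 7.56 | 0.731 | 0.672 |
| 4 | 11.20 | 9.63 | 8.51 | 0.729 | 0.667 |

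The between-groups F test has 1 and N-2 df, so it gives the two-visit row: 0.735 and 0.679. A normal approximation agrees: (1.960 + 0.842) x sqrt(38/50) - 1.960 = 0.48, which is power of about 0.685. Using the actual arm splits lowers the F-test figures by at most 0.003.

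**4. Detectable effect at 80% power.** To first order, 0.25 x sqrt(50/43) = 0.270 and 0.25 x sqrt(50/38) = 0.287. Allowing for the smaller error df gives 0.270 at 43 and 0.288-0.289 at 38.

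**5. If 50 included an unstated dropout allowance.** Calibrate 0.80 at 50 x (1 - a) and evaluate at 38:

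- a = 12% (44 analysable): 0.730-0.737
- a = 20% (40 analysable): 0.776-0.778
- a = 24% (38 analysable): 0.80

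**6. Power at 38 without the premise.** With f = 0.25 (assumed) and the formulas in step 2:

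| Visits | rho | Group x time | Between groups |
|---|---|---|---|
| 2 | 0.1 | 0.61 | 0.53 |
| 2 | 0.5 | 0.85 | 0.41 |
| 3 | 0.1 | 0.69 | 0.66 |
| 3 | 0.3 | 0.81 | 0.54 |
| 3 | 0.5 | 0.92 | 0.45 |
| 4 | 0.1 | 0.77 | 0.75 |
| 4 | 0.5 | 0.96 | 0.48 |

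Higher correlation helps the group x time test and hurts the between-groups test. The Results report both, so one power figure cannot serve for both.

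**The case against.** The strongest reply is that nothing here contradicts anything else. The 0.80 is a planning figure, the text never claims it was achieved, and 43 and 38 are openly reported. That is fair as far as it goes: the sample-size sentence is not shown to be miscalculated. But the stated size was not reached, and no text places the planning figure and the achieved size side by side.

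Second, 0.67-0.68 looks more precise than it is, since it assumes that 50 meant analysable participants at exactly 0.80. This stands. The figure can be quoted only with that condition attached, and the dropout-allowance cases belong beside it.

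Third, a reader might infer that the trial was underpowered. The documents do not support that. With three visits and rho 0.3 or more, the group x time test at 38 reaches 0.80 under f = 0.25. Nor do they support the opposite reassurance, because the between-groups test stays below 0.80 across the same inputs.

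A reader might also try to recover the correlation from the reported means, their ± values (taken as standard errors) and the time F statistics. I place no weight on that. For left lateral flexion (means 43.0, 46.3, 48.5; ± 1.1, 1.0, 1.3; F = 3.0), the error mean square would be 38 x 7.66 / 3.0 = 97.1 and the variance 38 x 1.30 = 49.4. The implied rho is 1 - 97.1/49.4 = -0.96, which is impossible for three visits. In any case, a correlation seen in the data would not reveal the one used in planning.

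Finally, Figure 1 and Tables 2-4 are not in the supplied text. Figure 1 may explain why 43 and not 50 were randomised, and the tables may already carry intervals. Neither absence can be asserted.

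**Conclusion.** The point holds in a limited form. The document states a size and power that the trial as run did not deliver, and the supplied text gives nothing in their place. The counts are certain.

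The cost in power is conditional. If 50 analysable participants give 0.80, power is about 0.73-0.74 at 43 and 0.67-0.68 at 38, with a detectable effect of about 0.29 at 38. If a 12-20% dropout allowance was built in, power at 38 is about 0.73-0.78. With f = 0.25 assumed, 2-4 visits and rho from 0.1 to 0.5, power at 38 spans 0.61-0.96 for group x time and 0.41-0.75 between groups.

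The width of those ranges is itself the reason to state the test and inputs. It is not evidence that 50 was wrong or that the trial lacked power.

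**What to change.** 1. Keep 0.80 as the planning figure for 50. State beside it that 43 were randomised (20 and 23) and 38 analysed (18 and 20), with the reason for the shortfall if Figure 1 does not give it.
2. Give the design-based power, or the detectable effect, at 38 for the planned effect and not the observed one. Do this separately for the group x time and between-groups tests, and list the inputs used. If the inputs behind 50 cannot be recovered, say so and give about 0.67-0.68 (detectable effect about 0.29), explicitly conditional on 50 giving 0.80.
3. Where Tables 2-4 do not already do so, give 95% confidence intervals for the non-significant between-group results: flexion, both rotations, PPT, NPRS, GROC and NDI. Reword the NDI sentence so that it reports a non-significant result and does not assert equality.

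The cost is a few sentences and intervals from data already held, with no new enrolment. The downside is that the stated power may become less favourable, and the inputs behind 50 may be lost.
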